5.2 Duration of exposure

Duration of exposure in days is defined as the last dose of investigational product – first dose of investigational product + 14 days.

5.3 Study Day and Study Period

If the visit date is on or after the first dose of IP administration:

- Study day = visit date – date of the first dose of IP administration + 1.

If the visit date is prior to the first dose of IP administration:

- Study day = visit date – date of the first dose of IP administration.

There are three analysis periods in this study: Screening (data collected before the first IP dose), Treatment (from first IP dose up to two weeks after the last IP dose) and Follow-up Period (from two weeks after the last IP dose up to the last measurement in the study).

5.4 Age

Unless specified, the age will be derived based on the informed consent date: Age = (Inform Consent Date – Birth Date +1)/365.25. The age will be rounded down to the nearest years, keeping 1 decimal place.

If birth date is missing, the birth date will be imputed to calculate age (See Section 7.3 for the algorithm to impute birth date).

5.5

[REDACTED]

[REDACTED]

[REDACTED]

[REDACTED]

[REDACTED]

[REDACTED]

[REDACTED]

[REDACTED]

5.6

[REDACTED]

[REDACTED]

[REDACTED]

[REDACTED]

[REDACTED]

[REDACTED]

[REDACTED]

5.7

[REDACTED]

[REDACTED]

[REDACTED]

[REDACTED]

5.8

[REDACTED]

[REDACTED]

[REDACTED]

[REDACTED]

5.9

5.10

5.11

[REDACTED]

[REDACTED]

[REDACTED]

[REDACTED]

[REDACTED]

[REDACTED]

[REDACTED]

[REDACTED]

5.12

[REDACTED]

[REDACTED]

6 ANALYSIS POPULATIONS

6.1 Safety Analysis Set

Safety analysis set will include all enrolled subjects who received any volume of UX053. The primary analysis will be performed on the Safety Analysis Set.

6.2 Per Protocol Analysis Set

The Per Protocol (PP) Analysis Set will exclude subjects from Safety Analysis Set with major protocol deviations that may impact PD or efficacy analysis. Reasons for exclusion will be documented for each subject. If deemed appropriate, a sensitivity analysis will be performed on the PP Analysis Set.

6.3 Pharmacokinetics Analysis Set

The Pharmacokinetics (PK) Analysis Set is the subset of subjects in the Safety analysis set who have at least 1 evaluable IP concentration. The PK analysis set will be used for the analysis of the PK endpoints.

7 STATISTICAL METHODS OF ANALYSES

7.1 General Principles

Descriptive statistics will be provided for selected demographics, safety, PK, and PD data. If a sufficient number of subjects with different disease subtypes are enrolled, subgroup summaries by disease subtype may be provided at the discretion of Ultragenyx. Continuous variables will be summarized by number of subjects and mean, SD and/or SE, median, minimum, and maximum values. Categorical variables will be summarized by number and percentage of subjects. Data will be summarized with descriptive statistics for the Screening Period.

The subject-level and cohort-level graphs of endpoints measurements over time will highlight the three periods of the study: Screening (data collected before the first IP dose), Treatment (from first IP dose up to two weeks after the IP dose) and Follow-up Period (from two weeks after the IP dose up to the last measurement in the study).

Although they are eligible, it is expected that few patients with GSD IIIb, IIIc, or IIId will enroll. Subjects with GSD IIIb/c/d will participate in all assessments, including muscle imaging and function tests, and will be included in all safety analyses. Sensitivity analyses for cardiac and skeletal muscle endpoints that exclude patients with GSD IIIb/c/d may be conducted.

The analysis will be presented by cohort and total group (Table 3). All raw data obtained from the CRFs will be included in data listings.

Table 2 Analysis Groups in the SAD Period

Cohort 1	Cohort 2	Total

7.2 Subject Accountability

The number and percentage of subjects in study populations will be summarized for each period. Subject disposition table will also include the number of subjects screened, and enrolled. No formal statistical comparisons will be performed.

Screen-failure subjects (ie, subjects screened but not enrolled) and the associated reasons for failure to enroll will be tabulated overall for the Screened Population. The reasons for premature discontinuation from study as recorded on electronic case report forms (eCRFs) will be summarized.

7.3 Protocol Deviations

Major and Minor Protocol deviations will be separately summarized by analysis group in each period. Both major and minor protocol deviations will be listed.

At the discretion of the Ultragenyx, major protocol violations may result in the removal of a subject's data from the PP Analysis Set. Ultragenyx will be responsible for producing the final protocol violation file; this file will include a description of the protocol violation, and clearly identify whether this violation warrants exclusion from the PP Analysis Set.

7.4 Extent of Exposure

The cumulative dose administered and duration of exposure will be summarized overall and by cohort.

7.5 Demographic and Baseline Characteristics

Demographic parameters (age, age group, race, ethnicity, sex, weight, height, and body mass index) and other baseline characteristics will be summarized descriptively by period and cohort.

7.6 Prior and Concomitant Medication

Prior medications are defined as medications with start date and end date before the first dose of IP.

Concomitant medications are defined as medications with end date on or after the first dose of IP or ongoing.

Both prior and concomitant medications will be coded by drug name and therapeutic class using World Health Organization (WHO) Drug Dictionary, version B3 September 2020. If a subject took a specific medication multiple times or took multiple medications within a specific therapeutic class, that subject will be counted only once for the coded drug name or therapeutic class.

Prior and Concomitant medication will be presented by analysis group in each period.

7.7 Analysis of Primary Endpoints

The primary analysis endpoint is the incidence and severity of TEAEs, serious TEAEs, and related TEAEs in the SAD and RD Periods. The primary analyses will be based on Safety Analysis Set and displayed by analysis group in each period.

Adverse events will be coded by system organ class and preferred term using the Medical Dictionary for Regulatory Activities (MedDRA version 23.1 or above).

An AE (classified by preferred term) will be considered a treatment emergent adverse event (TEAE) if it occurred on or after the first dose of investigational product and was not present prior to the first dose, or it was present at the first dose but increased in severity or frequency. TEAE will be separately reported in SAD and RD Period.

Subject incidence of TEAEs and percentages will be tabulated as the following:

- TEAEs by analysis group in each period, SOC and PT (preferred term) (sorted by descending frequency in the pooled UX053 group by SOC and PT)
- Related TEAEs by analysis group in each period, SOC and PT (sorted by descending frequency by SOC and PT)
- Serious TEAEs by analysis group in each period, SOC and PT (sorted by descending frequency by SOC and PT)
- Serious Related TEAEs by analysis group in each period, SOC and PT (sorted by descending frequency by SOC and PT).
- TEAE by greatest severity, SOC and PT
- Deaths by analysis group in each period, SOC and PT (sorted by descending frequency by SOC and PT).
- TEAEs leading to discontinuation of study by analysis group in each period, SOC and PT (sorted by descending frequency by SOC and PT).

Detailed listings for all AEs, serious TEAEs, AEs leading to the discontinuation of study, AEs leading to the discontinuation of treatment, and death will also be generated.

The severity of all AEs will be based on Common Terminology Criteria for Adverse Events (CTCAE), Version 5.0, published on November 27, 2017, unless the AE is Cytokine Release Syndrome (CRS), in which case the AE will be graded by the American Society for Transplantation and Cellular Therapy (ASTCT) Consensus Grading for CRS ([Lee et al. 2019](#)). If an AE cannot be graded based on CTCAE, the investigator will assign a severity based on 1 = mild, 2 = moderate, 3 = severe, 4 = life threatening, and 5 = Death.

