10.5.3. Continuous Glucose Monitoring

At the Screening Visit for the SAD cohort and ISV for the DB-RD cohort, each subject will receive a CGM and HHG device and be trained on how to use the device. For SAD cohorts, the CGM device will be worn from the Screening Visit until the End of Study (EOS) I D90/ET Visit ([Table 4](#)). For OL-RD cohorts, the continual glucose monitor will be worn from the OL-RD rescreening ISV to the Week 24 Visit, and for the week prior to the Week 36 and EOS II W48/ET Visits ([Table 5](#)). For DB-RD cohorts, the CGM will be worn for from ISV to the Week 24 Visit, and for the week prior to the Week 36 and EOS III W48/ET Visits ([Table 6](#)).

If the CGM device alarm notifies a subject that their blood sugar is abnormally high or low or the subject suspects their blood sugar is abnormally high or low, the subject will need to check their

blood sugar with a HHG that will be provided by Ultragenyx during screening (or rescreening, as applicable). If action is taken to rectify abnormal blood glucose levels, the event should be recorded as an AE ([Appendix 1](#) and [Appendix 2](#)).

When CGM data is being collected, all subjects will connect their CGM and HHG devices to a study-provided laptop weekly and upload CGM and HHG data. At remote visits, in conjunction with assessments performed by a home health nurse, the site will contact subjects by telephone or videoconference to confirm the CGM device is properly in use and data was uploaded; answer any questions regarding or help troubleshoot (if necessary) CGM device use; and review CGM data, HHG data (when applicable), and nutrition diary entries; outside of scheduled visits, these telephone calls will occur as needed. At in-clinic visits, a conversation between the site and the subject should occur to ensure CGM compliance and troubleshoot if needed.

Additional details regarding the CGM device are available in the Study Reference Manual.

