11.4. Safety Analyses

Safety variables including all AEs, SAEs, TEAEs, serious TEAEs, related TEAEs, safety laboratory assessments (full list available in [Appendix 3](#)), vital signs, weight, physical examination, clinical laboratory evaluations, and ECGs will be summarized for all subjects throughout the study and by treatment and cohort. Incidence and severity of IRRs and hypersensitivity reactions will also be summarized for all subjects throughout the study and by treatment and cohort. All AEs occurring from the onset of the study treatment infusion, and within 4 hours following the end of the infusion, regardless of the Investigator's assessment of whether or not the event was related to study drug administration will be considered an IRR.

All AEs will be coded according to the Medical Dictionary for Regulatory Activities (MedDRA) Version 23.0. The frequency and severity of all TEAEs, SAEs, and clinically relevant laboratory and ECG abnormalities will be reported by System Organ Class (SOC), by preferred term, and by relationship to study drug. All AEs reported with onset after the first dose of study drug (ie, TEAEs) will be included in the analysis. All SAEs will also be reported by relationship to study drug as reported by Investigator, seriousness, and outcome. For all AEs, SAEs, and treatment-related AEs, SAEs, the percentage of subjects who experienced at least 1 occurrence of the given event will be summarized for all subjects in the SAD cohorts and by treatment and cohort for the RD cohorts. Data summaries, listings, and narratives will be provided for subjects who died, discontinued treatment or withdrew from study due to an AE, or experienced SAEs, and any study procedure-related AEs.

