13. APPENDICES

APPENDIX 1. SAFETY DEFINITIONS AND ASSESSMENTS

Adverse Event (AE)

An AE is defined as any untoward medical occurrence associated with the use of a drug in humans, whether or not considered drug related. An AE can therefore be any unfavorable and unintended sign (including an abnormal laboratory finding, for example), symptom, or disease temporally associated with the use of a medicinal (investigational) product, whether or not related to the medicinal (investigational) products.

Pre-existing diseases or conditions will not be considered AEs unless there is an increase in the frequency or severity, or a change in the quality, of the disease or condition. Worsening of a pre-existing condition is considered an AE.

Any abnormal laboratory test results (hematology, clinical chemistry, or urine) or other safety assessments (eg, vital sign measurements), including those that worsen from screening/baseline that are felt to be clinically significant in the medical and scientific judgment of the Investigator are to be recorded as AEs.

Treatment-emergent AE (TEAE)

A TEAE is defined as any AE not present prior to the initiation of the drug treatment or any AE already present that worsens in either intensity or frequency following exposure to the drug treatment.

Serious Adverse Event (SAE)

An SAE is an AE that meets any of the following criteria in the view of either the Investigator or Ultragenyx:

- Death
- Life-threatening
 - *A life-threatening AE is an event that places the patient or subject at immediate risk of death. It does not include events that if it had occurred in a more serious or severe form might have caused death. For example, drug induced hepatitis that resolved without evidence of hepatic failure would not be considered life threatening even though drug induced hepatitis can be fatal.*
- Inpatient hospitalization or prolongation of existing hospitalization
 - *Hospitalization is defined by Ultragenyx as a full admission to hospital for a period of 24 hours or longer for diagnosis and treatment. This includes prolongation of an existing inpatient hospitalization. Examples of visits to a hospital facility that do not meet the serious criteria for hospitalization include:*
 - *Emergency room visits (that do not result in a full hospital admission)*
 - *Preplanned or elective procedures prior to study enrollment (eg, outpatient surgery)*
 - *Protocol procedures*

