such as “erythema,” “rash,” or “lump on head” should be avoided and more specific information should be provided, such as “erythematous macule on right leg,” “allergic dermatitis,” or “scalp cyst.”

Adverse Events Occurring Secondary to Other Events

In general, AEs occurring secondary to other events (eg, cascade events or clinical sequelae) should be identified by their primary cause. For example, if severe diarrhea is known to have resulted in dehydration, it is sufficient to record only diarrhea as the AE on the CRF and, if also serious, on the SAE form. However, medically significant AEs occurring secondary to an initiating event that are separated in time should be recorded as independent events on the CRF. For example, if a severe gastrointestinal hemorrhage leads to renal failure, both events should be recorded separately on the CRF.

Persistent or Recurrent Adverse Events

A persistent AE is one that extends continuously, without resolution between patient evaluation time points. Such events should only be recorded once in the CRF unless their severity increases. If a persistent AE becomes more severe, it should be recorded again on the CRF.

A recurrent AE is one that occurs and resolves between patient evaluation time points and subsequently recurs. All recurrent AEs should be recorded individually on the CRF.

Abnormal Laboratory Values

Only clinically significant laboratory abnormalities in the opinion of the Investigator are to be recorded as AEs on the CRF and SAE form (if applicable). For example, abnormalities that require study drug dose modification, discontinuation of study treatment, more frequent follow-up assessments, or further diagnostic investigation may be considered clinically significant by the Investigator.

If the clinically significant laboratory abnormality is a sign of a disease or syndrome (eg, alkaline phosphatase and bilirubin 5 × upper limit of normal (ULN) associated with cholecystitis), only the diagnosis (eg, cholecystitis) needs to be recorded on the CRF and the SAE form (if applicable).

If the laboratory abnormality can be characterized by a precise clinical term, the clinical term should be recorded as the AE or SAE. For example, an elevated serum potassium level of 7.0 mEq/L should be recorded as “hyperkalemia.”

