1 INTRODUCTION

The purpose of this Statistical Analysis Plan (SAP) is to provide details of the statistical analyses that have been outlined within the UX053-CL101 Protocol dated 3 January 2022. Changes from these guidelines must be substantiated by sound statistical reasoning and documented in the clinical study report (CSR).

Should there be a difference between the SAP and the protocol with respect to data analysis, the SAP will take precedence over the protocol.

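### As worded, SAP 7.7 does not count a post-dose event as a TEAE if its preferred term was already reported and resolved in screening

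*SAP*

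**What the plan says.** SAP 7.7 makes TEAEs the primary endpoint: "The primary analysis endpoint is the incidence and severity of TEAEs, serious TEAEs, and related TEAEs in the SAD and RD Periods". Its definition begins "An AE (classified by preferred term) will be considered a treatment emergent adverse event (TEAE) if it occurred on or after the first dose" and continues with two alternatives: the event "was not present prior to the first dose, or it was present at the first dose but increased in severity or frequency".

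The protocol has two statements of its own. Section 11.4 (Safety Analyses) uses onset alone: "All AEs reported with onset after the first dose of study drug (ie, TEAEs) will be included in the analysis". Appendix 1 (Safety Definitions and Assessments) defines a TEAE as "any AE not present prior to the initiation of the drug treatment or any AE already present that worsens in either intensity or frequency" after exposure, with no reference to preferred terms.

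On conflicts, SAP section 1 states that for data analysis "the SAP will take precedence over the protocol". SAP section 8, which lists changes to the protocol's analyses, mentions only the early termination after 4 subjects in Cohort 1S and 4 in Cohort 2S, and limits reporting to those cohorts.

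Three collection rules bear on the point. Protocol Appendix 2 (Table 14) collects AEs from signature of the consent form. The same appendix says of events that resolve and come back: "All recurrent AEs should be recorded individually on the CRF". Protocol 10.5.3 has SAD subjects wear a glucose monitor from the Screening Visit and says: "If action is taken to rectify abnormal blood glucose levels, the event should be recorded as an AE".

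**The concern.** The SAP's two conditions do not cover every case. One asks whether the term was absent before the first dose. The other asks whether it was there at dosing and then increased. A term that came and went during screening lies between them: it was present earlier, but not at dosing. If it returns after the infusion it is not a TEAE on the SAP's wording, whatever its grade.

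The pattern can plausibly arise here. AEs are recorded from consent, treated low glucose is an AE, and two of the three alternative routes in inclusion criterion 2 are a history of hypoglycemia. The same definition feeds the overall, related, serious, serious related and greatest-severity TEAE tables. An event lost at this step is therefore lost from all the tabulated primary results, in a first-in-human trial where under-counting is the less cautious error.

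**Working it through.** **1. The definitions side by side.** Each possible course of a preferred term, taken through the wording:

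| Course of the term | SAP 7.7, by preferred term | Protocol 11.4, onset only |
|---|---|---|
| First appears after dosing | TEAE | TEAE |
| Resolved in screening, recurs at same grade | not TEAE | TEAE |
| Resolved in screening, recurs at higher grade | not TEAE | TEAE |
| Ongoing at dosing, unchanged | not TEAE | not TEAE |
| Ongoing at dosing, worsens | TEAE | not by onset alone; Appendix 1 covers it |

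The second and third rows are the gap. No other readable part of the SAP closes it.

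**2. The plan's own figures.** The only numbers tied to TEAE counting are the detection probabilities in SAP 3.5. The formula is 1 − (1 − p)^n, with n subjects and true incidence p.

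- n = 10, p = 0.20: 1 − 0.80^10 = 0.893 (stated 89%).
- n = 22, p = 0.10: 1 − 0.90^22 = 0.902 (stated 90%).

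Both reproduce. They assume that every subject who has the event is counted.

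**3. Effect of masking on detection.** Let m be the share of affected subjects whose event is masked by a same-term event in screening. The documents give no value, so m is an assumption. The effective incidence is p(1 − m). For the 8 enrolled subjects and p = 0.20:

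- m = 0: 1 − 0.80^8 = 83.2%
- m = 10%: 1 − 0.82^8 = 79.6%
- m = 25%: 1 − 0.85^8 = 72.8%
- m = 50%: 1 − 0.90^8 = 57.0%

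**4. Effect on reported incidence.** With 4 subjects per cohort, one masked subject is 1/4 = 25 percentage points of that term's cohort incidence.

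**5. Illustration tied to the schedule.** Protocol 7.2.1 gives about 2 weeks of SAD screening and 90 days of follow-up. Assume one constant daily event rate λ for all subjects before and after dosing, with every screening event recorded and resolved by dosing. Take an assumed true post-dose incidence of 90%.

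- λ = −ln(1 − 0.90)/90 = 2.303/90 = 0.0256 per day.
- Chance of at least one screening event: 1 − exp(−0.0256 × 14) = 30%.
- Counted incidence: 0.90 × (1 − 0.30) = 63%.

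Larger losses need a higher rate before dosing than after. For 50% of subjects to have a screening event, the daily rate must be −ln(0.5)/14 = 0.0495, about 1.9 times the post-dose rate. For 80% it must be −ln(0.2)/14 = 0.115, about 4.5 times.

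**The case against.** The strongest reply is that the SAP can be read record by record. Recurrences are separate CRF records, so a new post-dose episode is an AE that was not there before dosing, and it meets the first condition. Other SAP rules work per record on dates: 10.1.3 imputes AE start dates relative to the first dose, and 10.1.4 assigns missing causality to any AE starting on or after that dose. The mention of preferred terms directly follows the MedDRA coding sentence and may only describe coding. This reading is possible, but it leaves the parenthesis without effect. Two programmers could then produce different primary tables.

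Second, the absence-before-treatment condition is the protocol's own, because Appendix 1 contains it. That is correct. What the SAP adds is the preferred-term level and the requirement that the event be there at dosing, where Appendix 1 says only that it already existed. Because frequency has meaning mainly for a recurring term, one could argue that the second condition was meant to catch a term that returns worse. The wording still ties it to presence at dosing, and a recurrence at the same grade and frequency would be missed on either view.

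Third, leaving unchanged background disease out of emergent counts is a defensible choice in an uncontrolled, descriptive study. That holds for unchanged events. It does not explain dropping a recurrence at a higher grade, and SAP section 8 does not declare the choice.

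**Conclusion.** The gap is real on the plain wording, and the governing document is the narrower one. It affects only post-dose events whose preferred term was also reported and resolved between consent and first dose. It bears on the primary endpoint for the two cohorts to be reported. Its size cannot be determined from the documents. The 63% figure rests on the constant-rate assumption and an assumed 90% incidence, and the detection figures rest on assumed values of m.

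The documents do not support four stronger readings that a reader might infer:

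- That recurrent post-dose events drop out in general. A term first seen after dosing counts however often it recurs, so new reactions, including infusion reactions under new terms, are unaffected.
- That same-term screening events are the norm. SAD screening lasts only about 2 weeks, one eligibility route is raised ALT alone, Appendix 1 does not treat unchanged pre-existing conditions as AEs, and no screening AE rate is given.
- That most of the incidence would be lost. That needs the pre-dose rates shown above, well beyond the post-dose rate, and nothing in the documents suggests them.
- That the events vanish. SAP 7.7 lists all AEs, so they remain visible by subject, although not in the TEAE tables.

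**What to change.** Replace the definition in SAP 7.7 with one that works per AE record: a TEAE is any AE with onset at or after the start of the first infusion, or any AE ongoing at first dose that worsens in severity or frequency afterwards. Delete the parenthesis on preferred terms and the condition that the event be absent before the first dose. Preferred terms remain the level for tabulation.

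This follows Protocol 11.4 for onset and keeps the worsening part of Appendix 1. It does not reproduce Appendix 1's wording, which has its own absence-before-treatment condition, so the SAP should state that Appendix 1 is applied per AE record.

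The cost is one definition and one clarifying line. No new data are needed and no sample-size figure changes. TEAE counts may be slightly higher, because recurrent background disease events will be included.
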